14.3. Analysis Populations

Per-Protocol Population:

Per-protocol population will consist of all subjects who have successfully completed all visits and did not substantially deviate from the protocol as determined by the trial cohort review committee prior to database hard lock. Justification of excluding subjects with protocol deviations in the per-protocol population set will be documented in a memo to file.

A sensitivity analysis will be conducted on all subjects who were administered any test article excluding subjects who drop out prior to administering any test article. At least one observation should be recorded.

14.4. Level of Statistical Significance

All planned analysis will be conducted with an overall type I error rate of 5% for the primary and secondary hypotheses. Unless otherwise specified, all statistical tests will be 2-sided.

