2.3. Hypotheses

2.3.1. Primary Hypotheses

The Test lens will be non-inferior to the Control 1 lens with respect to overall night driving performance. A non-inferiority margin of -0.25 will be used.

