2.3.2. Secondary Hypotheses

1. The Test lens will be non-inferior to the Control 1 lens with respect to binocular low luminance high contrast visual acuity. A non-inferiority margin of 0.1 LogMAR will be used
2. The Test lens will be no different than the Control 1 with respect to low luminance low contrast threshold without glare.
3. The Test lens will be no different than Control 1 with respect to the percentage of roads signs correctly identified at night driving.
4. The Test lens will be no different to Control 1 with respect to the average distance to correctly identify a pre-determined road sign at night driving.
5. The Test lens will be no different than the Control 1 with respect to the percentage of hazards avoidance at night driving.
6. The Test lens will be no different than the Control 1 with respect to average pedestrian recognition distance at night driving.

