1. INTRODUCTION

1.1. Background

This document describes the data analysis specifications for study protocol CR-5830 titled "Evaluating the impact of JJVC senofilcon A-based contact lens with new UV-blocker on day and night driving performance" Version 3.0 Amendment 2.0 dated on September 14th, 2017. The test article is the JJVCI Investigational Contact Lens senofilcon A-based with new UV-blocker while the two controls are ACUVUE® OASYS® brand contact lens with HYDRACLEAR® Plus worn with spectacle frame without lenses (Control 1) and ACUVUE® OASYS® brand contact lenses with HYDRACLEAR® Plus worn with Transitions® XTRActiveTM- gray spectacles (Control 2)

This document will serve as the final guidance for all the statistical analysis for this study and will supersede section 14 in the protocol if there are any discrepancies (i.e. See Amendment History section)

The study aims to investigate the effect of senofilcon A contact lenses with new UV-blocker on vision and driving performance in both daytime and nighttime lighting under real world driving conditions. This will be achieved through field-based driving studies on a closed-road driving circuit at night and during the day. Quantitative methods will be used to assess vision and driving performance under a range of challenging conditions and appropriate masking, order of testing randomization and control conditions will be used.

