2.1. Level of Statistical Significance

All planned analysis will be conducted with an overall type I error rate of 5%. Unless otherwise specified, all statistical tests will be 2-sided.

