5.2. Primary Analysis Methods

Overall driving performance score will be analyzed using a linear mixed model; sequence of lens wear, period, lens type, first order carry-over, driving time (day or night) and the 2-way interactions: lens*time, sequence*time, period*time and carry*time will be included in the model as fixed effects. Age will be included as fixed covariate when appropriate. An appropriate covariance structure will be selected to model the correlation between measurements across periods within the same subject and driving time. Covariance structures that will be considered include:

- Compound Symmetry (CS)
- Heterogeneous Compound Symmetry (CSH)
- Unstructured (UN)
- Ante-dependence (ANTE(1))

For ANTE(1) structure, subject and driving time nested within subject will be included in the model as random effects. For the remaining structures only subject will be included as random effect. The covariance structure that returns the lowest Akaike Information Criteria Corrected (AICC) will be selected as the structure that best fit the data¹². Heterogeneous residuals covariance structures (R-side) across driving time will be considered when appropriate. The log-likelihood ratio test will be used to test for the homogeneity between the residual covariance structures. The Kenward and Roger method will be used for the denominator degree of freedom. Non-significant interactions at the 15% significance level will be excluded from the model. The interaction between lens type and driving time will be forced into the final model.

Comparisons between Test and Control 1 will be conducted overall across driving time and within each level of driving time. Results from the final selected model will be reported as least-square mean (LSM) differences with 95% confidence intervals.

The null and alternative hypotheses for non-inferiority of Test lens relative to Control 1 are as follows:

$$H_0: \mu_T - \mu_C \le -0.25 H_A: \mu_T - \mu_C > -0.25,$$

where μ_T and μ_C are the means of night driving performance score for Test and Control 1, respectively. Non-inferiority of the Test relative to Control 1 will be concluded if the lower limit of the 95% confidence interval of the LSM difference between Test and Control 1, at night driving time, is greater than - 0.25.

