For ANTE(1) structure, subject and driving time nested within subject will be included in the model as random effects. For the remaining structures only subject will be included as random effect. The covariance structure that returns the lowest Akaike Information Criteria Corrected (AICC) will be selected as the structure that best fit the data¹². Heterogeneous residuals covariance structures (R-side) across driving time will be considered when appropriate. The log-likelihood ratio test will be used to test for the homogeneity between the residual covariance structures. The Kenward and Roger method will be used for the denominator degree of freedom. Non-significant interactions at the 15% significance level will be excluded from the model. The interaction between lens type and driving time will be forced into the final model.

Results from the final selected model will be reported as least-square mean (LSM) estimates with 95% confidence intervals.

The null and alternative hypotheses for non-inferiority of Test lens relative to Control 1 are as follows:

$$H_0: \mu_T - \mu_C = 0$$

$$H_A: \mu_T - \mu_C \neq 0,$$

where $\mu_T - \mu_C$ is the mean difference of distance recognition at night driving between Test and Control 1. No statistical difference between Test and Control 1 will be concluded if 0 falls within the 95% confidence interval of the LSM difference between Test and Control 1.

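### The plan promises an overall 5% type I error for the primary and secondary hypotheses, but the five secondary difference tests are unadjusted and take the total above 5%

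*Protocol*

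**What the plan says.** Protocol 14.4 gives the error rate: "All planned analysis will be conducted with an overall type I error rate of 5% for the primary and secondary hypotheses". It adds: "Unless otherwise specified, all statistical tests will be 2-sided". SAP 2.1 drops the reference to primary and secondary hypotheses but keeps the word overall: "All planned analysis will be conducted with an overall type I error rate of 5" per cent. SAP 1.1 says that the SAP "will supersede section 14 in the protocol if there are any discrepancies", but since SAP 2.1 still promises an overall rate, that rule does not settle the matter.

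Protocol 2.3 and SAP 1.4 list seven hypotheses of Test against Control 1:

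- One primary, on the night driving score: "A non-inferiority margin of -0.25 will be used".
- One secondary non-inferiority hypothesis, on low-luminance high-contrast acuity, with a margin of 0.1 logMAR.
- Five secondary hypotheses of no difference: contrast threshold without glare, percentage of signs identified, sign recognition distance, percentage of hazards avoided, and pedestrian distance. The last reads "The Test lens will be no different than the Control 1 with respect to average pedestrian recognition distance at night driving".

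Each has its own decision rule on a 95% interval. For the primary, SAP 5.2 says "Non-inferiority of the Test relative to Control 1 will be concluded if the lower limit of the 95% confidence interval of the LSM difference" lies above the margin. For the two distances, SAP 6.2 says "No statistical difference between Test and Control 1 will be concluded if 0 falls within the 95% confidence interval". The contrast, sign and hazard rules are the same with 1 in place of 0.

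Neither document gives an order of testing, a gatekeeping rule, an alpha split or an adjusted interval for these seven. In SAP Appendix A, the ESTIMATE statements for the primary and secondary comparisons carry no adjustment option. The only adjustment is Bonferroni on comparisons classed as other analysis. The text of SAP 7 applies it to the driving-score comparisons in hypotheses 1 and 2 of that section. The Appendix A code also applies it to the other-analysis comparisons of signs, hazards and distances. None of these is among the seven.

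**The concern.** An overall rate attached to a named set of hypotheses is naturally read as the chance of any false rejection within that set. The documents have different wording for the per-comparison case: SAP 7 gives its remaining hypotheses a two-sided 5% rate and leaves out the word overall. The plan thus adjusts some lower-ranked comparisons and leaves unadjusted the family to which the 5% promise is attached.

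At stake is the accuracy of the error statement in a study that, by SAP 1.2, is meant to support a 510(k) submission. A chance difference in sign, hazard or pedestrian performance could be reported under an overall 5% guarantee that the rules do not provide.

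**Working it through.** **Inputs.** Two non-inferiority tests (Protocol 2.3.1 and item 1 of 2.3.2). Each reads one limit of a 95% interval against a margin, so each is a one-sided 2.5% test. Five difference tests (items 2 to 6 of Protocol 2.3.2), each two-sided at 5%. The promised figure is 5% overall.

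**Two non-inferiority tests, true effects at the margins.**
- Independent: 1 − 0.975² = 1 − 0.9506 = 4.9%.
- Upper bound under any dependence: 0.025 + 0.025 = 5.0%.

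The promised 5% is met for this pair, but only for this pair.

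**Five difference tests, no true difference.**
- Independent: 1 − 0.95⁵ = 1 − 0.7738 = 22.6%.

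**All seven, the five differences zero and both non-inferiority effects exactly at their margins.**
- Independent: 1 − 0.975² × 0.95⁵ = 1 − 0.7356 = 26.4%.
- Upper bound under any dependence: 2 × 0.025 + 5 × 0.05 = 30%.

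**Correlated statistics.** The documents give no correlations between endpoints, so a range is assumed: normal test statistics with one common correlation.

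| Common correlation | Two non-inferiority tests | Five difference tests | All seven |
|---|---|---|---|
| 0 | 4.9% | 22.6% | 26.4% |
| 0.3 | 4.8% | 21% | 24% |
| 0.5 | 4.5% | 18% | 21% |
| 0.7 | 4.2% | 15% | 16% |
| 0.9 | 3.5% | 10% | 11% |

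At every correlation tried, up to 0.9, the five and the seven stay above 5%.

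**Would wider intervals help?** Bonferroni over seven gives 0.05/7 = 0.00714 each, that is, 99.29% intervals. For the five difference endpoints the plan draws its hoped-for conclusion when the interval covers 0 or 1. If the true difference is 2 standard errors, the chance of concluding no difference is 48% with a 95% interval and 76% with a 99.29% interval. Widening the intervals makes that conclusion easier to reach when it is false.

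**The case against.** The strongest reply is that the error that matters most is already controlled. The chance of any false non-inferiority conclusion is at most 5% in total, and the single primary hypothesis keeps its own one-sided 2.5% whatever happens to the secondaries. For the other five, a type I error is a false difference, which goes against the hypothesis that the sponsor has stated. All of this stands.

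It also stands that 26% is the top of the independent case and rests on an unlikely joint null. Four of the five difference endpoints are components of the six-measure primary score (Protocol 2.2.1). If those four show no difference and the composite sits at −0.25, lane keeping and lap time must average 6 × (−0.25) / 2 = −0.75 Z each. Measures from the same drives are also unlikely to be independent. The 22.6% for the five alone needs no such scenario, though it too assumes independence.

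A reader might infer that the primary conclusion is inflated, that there is a 26% chance of a false claim in favour of the Test lens, or that an acuity claim after a failed primary breaks the 5% limit. The documents support none of these: the two non-inferiority tests already share no more than 5%, and the excess consists of false differences.

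The reply does not remove the mismatch. Protocol 14.4 attaches the overall 5% to all the secondary hypotheses, including these five.

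**Conclusion.** The concern holds as a false statement of error control, wrong as written, and not as a flaw in the primary test. No procedure in either document delivers an overall 5% for the seven hypotheses. The excess arises from the five difference tests: 22.6% if they are independent and no true difference exists, falling to about 10% at a common correlation of 0.9. For all seven the figure is about 26% under independence with both non-inferiority effects at their margins, and about 24% to 11% for common correlations of 0.3 to 0.9. The correlations are assumptions.

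A separate limit follows from the working. Type I control does not protect a conclusion of no difference, so a multiplicity adjustment would not give those five conclusions the support that they lack.

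**What to change.** Preferred change:

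- In Protocol 14.4 and SAP 2.1, limit the overall 5% statement to the two non-inferiority tests against Control 1 (night driving score and low-luminance acuity), each at one-sided 2.5%.
- Report the other five secondary endpoints as estimates with 95% intervals and no confirmatory claim.
- Amend the hypotheses in Protocol 2.3.2 and SAP 1.4.2, and the decision rules in Protocol 14.6 and SAP 6.2, so that they agree with this.

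Alternative: in Protocol 14.4 and SAP 2.1, replace the overall 5% wording with 5% two-sided per comparison, with no adjustment across the primary and secondary hypotheses.

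Testing acuity only after the primary is met is optional; the 5% limit on the pair does not need it.

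The cost is wording in both documents. Under the preferred change, five prespecified hypotheses become descriptive. The primary test, its power and the sample size stay as they are.

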14.5. Primary Analysis

Overall Driving Performance score

Overall driving performance score will be analyzed using a linear mixed model; sequence of lens wear, period, lens type, first order carry-over, driving time (day or night) and the interactions between lens type by driving time and period by driving time will be included in the model as fixed effects. Age will be included as fixed covariate when appropriate. An appropriate covariance structure will be selected to model the correlation between measurements across periods within the same subject and driving time. Covariance structures that will be considered include:

- Compound Symmetry (CS)
- Heterogeneous Compound Symmetry (CSH)
- Unstructured (UN)
- Ante-dependence (ANTE(1))

For ANTE(1) structure, subject and driving time nested within subject will be included in the model as random effects. For the remaining structures only subject will be included as random effect. The covariance structure that returns the lowest Akaike Information Criteria Corrected

(AICC) will be selected as the structure that best fit the data¹¹. Heterogeneous residuals covariance structures (R-side) across driving time will be considered when appropriate. The log-likelihood ratio test will be used to test for the homogeneity between the residual covariance structures. The Kenward and Roger method will be used for the denominator degree of freedom.

Comparisons between Test and Control 1 will be conducted overall across driving time and within each level of driving time. Results from the final selected model will be reported as least-square mean (LSM) differences with 95% confidence intervals.

The null and alternative hypotheses for non-inferiority of Test lens relative to Control 1 are as follows:

$$\begin{aligned} H_0: \mu_T - \mu_C &\leq -0.25 \\ H_A: \mu_T - \mu_C &> -0.25, \end{aligned}$$

where μ_T and μ_C are the means of night driving performance score for Test and Control 1, respectively. Non-inferiority of the Test relative to Control 1 will be concluded if the lower limit of the 95% confidence interval of the LSM difference between Test and Control 1, at night driving time, is greater than - 0.25.

14.6. Secondary Analysis

Binocular distance visual acuity (LogMAR)

Binocular low luminance high contrast distance visual acuity will be analyzed using a linear mixed model to test for the difference between Test and Control 1. Sequence of lens wear, period, lens type, first order carryover effect will be included in the model as fixed effects. An appropriate covariance structure will be chosen to model the residual errors between measurements within the same subject across periods. Covariance structures considered will be:

- Compound Symmetry (CS)
- Heterogeneous Compound Symmetry (CSH)
- Unstructured (UN)
- Ante-dependence (ANTE(1))

For ANTE(1) structure, subject will be included in the model as random effects. The covariance structure that returns the lowest AICC will be selected as the structure that best fit the data.

The null and alternative hypotheses for non-inferiority of Test lens relative to Control 1 are as follows:

$$\begin{aligned} H_0: \mu_T - \mu_C &\geq 0.1 \\ H_A: \mu_T - \mu_C &< 0.1, \end{aligned}$$

where $\mu_T - \mu_C$ is the mean difference between Test lens and Control 1 lens. Non-inferiority of the Test lens relative to the Control 1 lens will be concluded if the upper limit of the 95% confidence interval of the LSM difference between Test and Control 1 is less than 0.1.

Low luminance contrast threshold

Low luminance contrast threshold will be analyzed using a Poisson generalized linear mixed model for count data. Sequence, period, lens type, first order carry-over, contrast level and the interaction contrast level by lens type will be included as fixed effects and subject as random effect. An unstructured covariance matrix (UN) will be used to model the correlation between measurements from the same subject and period across contrast level. A negative binomial distribution will be considered if the data is over-dispersed.

The null and alternative hypotheses for no-difference between Test and Control 1 are as follows:

$$\begin{aligned} H_0: \lambda_T/\lambda_C &= 1 \\ H_A: \lambda_T/\lambda_C &\neq 1, \end{aligned}$$

where λ_T/λ_C is the ratio of the average number of correctly identified orientation of the Landolt C. No statistical difference between Test lens and Control 1 lens will be concluded if 1 falls within the 95% confidence interval of the LSM ratio, λ_T/λ_C , of Test over Control 1.

Sign Recognition and Hazard Avoidance (%)

Proportion of correctly identified signs and proportion of hazard avoidance will be analyzed separately using a generalized linear mixed model with beta distribution and logit link function. Each model will include sequence, period, lens type, first order carry-over, driving time (day or night), and the interactions lens type by driving time and period by driving time as fixed effect factors. An unstructured covariance matrix (UN) will be used to model the correlation between measurements from the same subject across periods.

The null and alternative hypotheses for no-difference between Test and Control 1 are as follows:

$$\begin{aligned} H_0: OR &= 1 \\ H_A: OR &\neq 1, \end{aligned}$$

where OR is the odds ratio of hazard avoidance at night driving time of Test over Control 1. No statistical difference between Test and Control 1 will be concluded if 1 falls within the 95% confidence interval of the odds ratio.

Pedestrian Distance Recognition and Road Sign Recognition

Pedestrian distance recognition and road sign recognition distance (or log-transformed distance) will be analyzed separately using a linear mixed model; sequence of lens wear, period, lens type, first order carry-over, driving time (day or night), and the interactions between lens type by driving time and period by driving time will be included in the model as

fixed effects. Age will be included as fixed covariate when appropriate. An appropriate covariance structure will be selected to model the correlation between measurements across periods within the same subject and driving time. Covariance structures that will be considered include:

- Compound Symmetry (CS)
- Heterogeneous Compound Symmetry (CSH)
- Unstructured (UN)
- Ante-dependence (ANTE(1))

For ANTE(1) structure, subject and driving time nested within subject will be included in the model as random effects. For the remaining structures, only subject will be included as random effect. The covariance structure that returns the lowest Akaike Information Criteria Corrected (AICC) will be selected as the structure that best fit the data¹¹. Heterogeneous residuals covariance structures (R-side) across driving time will be considered when appropriate. The log-likelihood ratio test will be used to test for the homogeneity between the residual covariance structures. The Kenward and Roger method will be used for the denominator degree of freedom.

Results from the final selected model will be reported as least-square mean (LSM) estimates with 95% confidence intervals.

The null and alternative hypotheses for non-inferiority of Test lens relative to Control 1 are as follows:

$$H_0: \mu_T - \mu_C = 0$$
$$H_A: \mu_T - \mu_C \neq 0,$$

where $\mu_T - \mu_C$ is the mean difference of distance recognition at night driving between Test and Control 1. No statistical difference between Test and Control 1 will be concluded if 0 falls within the 95% confidence interval of the LSM difference between Test and Control 1.

14.7. Other Exploratory Analyses

No exploratory analysis is planned for this study. Further analysis may be conducted at the discretion of the study responsible clinician at the end of the study.

14.8. Interim Analysis

There will not be an interim analysis performed for this study.

14.9. Procedure for Handling Missing Data and Drop-Outs

Missing or spurious values will not be imputed as the number of missing values is expected to be low the count of missing values will be included in the summary tables and listings. Dropout is expected to be one of the main reasons of missing data in this trial. Past soft contact lens clinical trials don't provide any evidence that subjects dropout is systematic or not at random.

14.10. Procedure for Reporting Deviations from Statistical Plan

The analysis will be conducted according to that specified in above sections. There are no known reasons for which it is planned to deviate from these analysis methods. If for any reason a change is made, the change will be documented in the study report along with a justification for the change.

